8.4.5. Chest X-Ray and Tuberculosis Testing

However, patients with a PPD skin test ≥ 5 mm induration or a positive QuantiFERON®-TB Gold or positive T-SPOT® test at screening, and patients who have documentation of a history of a positive TB test but do not have documentation of a history of at least 4 weeks of appropriate latent TB treatment, but no other evidence of active TB, may be rescreened 1 time and may be enrolled without repeating a PPD or QuantiFERON®-TB Gold test or T-SPOT® if the following conditions are met:

- after receiving at least 4 weeks of appropriate latent TB infection (LTBI) therapy prior to rescreening, with commitment by the patient and the investigator for the patient to complete a full course of prophylaxis for TB

9.3.2. Adjustment for Multiple Comparisons

A multiple testing strategy for the primary and the major secondary endpoints will be implemented to control the family-wise type I error rate at a 2-sided α level of 0.05. The following primary and major secondary endpoints will be sequentially tested in the following order to compare ixekizumab Q2W versus placebo, using the primary analysis method:-

- Primary (Test 1) – Proportion of patients achieving sPGA of Genitalia (0,1) at Week 12
- ~~Major Secondary – Mean change from baseline in the genital psoriasis itch NRS item within the GPSS at Week 12~~
- Major Secondary 1 (Test 2) – Proportion of patients achieving overall sPGA (0,1) at Week 12
- Major Secondary 2 (Test 3) – Proportion of patients achieving a meaningful change from baseline in the genital psoriasis itch NRS item within the GPSS at Week 12
- Major Secondary 3 (Test 4) – Proportion of patients whose frequency of sexual activity is never limited by genital psoriasis, an item score of 0, at Week 12

The primary endpoint (Test 1) will be tested at 2-sided $\alpha = 0.05$. ~~If the test for primary endpoint is significant, then the test for the major secondary endpoint will be performed. Otherwise the testing will stop.~~ If Test 1 is significant, then Test 2 will be tested at the 2-sided $\alpha = 0.05$. Similarly, Test 3 and Test 4 will be performed only if all prior tests are significant. If a test is not significant, all subsequent tests are not significant.

9.4.2. Patient Characteristics

Baseline clinical and PRO measurements will include sPGA of Genitalia score, mGPASI total score, overall sPGA, overall PASI, BSA, BSA category (<10% versus \geq 10% baseline BSA involvement), GPSS total and item scores (including Genital Psoriasis Itch NRS), DLQI total score, GPSIS subscales, SFQ items, PatGA-Genital, Touch avoidance NRS, SF-36, QIDS-SR16, and CAPP.

9.5.2. Secondary Analyses

- **Categorical**
 - Secondary analysis on the categorical efficacy and health outcome variables will be conducted using a Fisher's exact test, using the NRI method.
 - A categorical, pseudo-likelihood-based MMRM for categorical repeated measures analysis may also be performed for the primary endpoint of sPGA of Genitalia (0, 1). The details of the analysis model will be presented in the SAP.
- **Continuous**
 - Secondary analyses for treatment comparisons on continuous efficacy and health outcome variables will be conducted using an analysis of covariance (ANCOVA) model and LOCF or mBOCF imputation methods. The ANCOVA model will include treatment, baseline BSA category, and baseline value. Type III sums of squares for the LS means will be used for the statistical comparison; the 95% CI will be reported.

9.6.1. Adverse Events

In addition to general safety parameters, safety information on specific topics of special interest will also be presented. Potential AESIs will be identified by a standardized MedDRA query (SMQ) or a Lilly defined MedDRA PT listing. The details of the AESIs will be defined in the SAP.

9.8.2. Immunogenicity Analyses

The frequency and percentage (incidence) of patients with positive, negative, or inconclusive ADA at baseline and patients with positive, negative, or inconclusive TE-ADA postbaseline will be summarized by treatment group. Additional summarizations for patients who are TE-ADA+ will be done for ~~patients who are TE-ADA persistent or transient positive;~~ patients who are NAb positive, negative, or inconclusive; and for TE-ADA titers.

Assessment of immunogenicity with respect to safety will include comparison of patients who experience TEAEs of systemic allergy/hypersensitivity and of injection-site reactions and also

develop treatment-emergent ADA positive status with patients who experience the same types of TEAEs but who remain treatment-emergent ADA negative. TE-ADA titers will also be evaluated in patients who experience these events.

Appendix 2. Schedule of Activities

Schedule of Activities, Protocol I1F-MC-RHBQ

	Screening		Baseline Randomization	Blinded Treatment Dosing Period (Period 2)				
CRF Visit (V) Number	V1		V2	V3	V4	V5	V6	V7
Weeks since Randomization			W0	W1	W2	W4	W8	W12
Study Days	-30 to -7 d	V1A: 2-3 d post-V1	1	7 ± 2d	14 ± 2d	28 ± 2d	56 ± 2d	84 ± 4d
Inclusion/exclusion criteria ^d	X		X					
Laboratory Tests								
GPSS ^k	Daily from Screening (V1) to Week 12 (V7)							X
GPSIS ^k	Weekly from Screening (V1) to Week 12 (V7)							X
SFQ ^k	Weekly from Screening (V1) to Week 12 (V7)							X
Fasting Lipid panel ^f			X			X		X

	Open-Label Treatment (Period 3)					ETV	Post-Treatment Follow-Up (Period 4) ^x		
							Required Follow-Up Visits		As-Needed Follow-Up Visits
CRF Visit (V) Number	V8	V9	V10	V11	V12	ETV _y	V801	V802	V803 ^z and onward
Weeks since Randomization	W16	W24	W28	W40	W52		LV + 4W	LV + 12W	LV + 24W
Study Days	112 ± 7d	168 ± 7d	196 ± 7d	280 ± 7d	364 ± 7d				
Laboratory Tests									
Fasting Lipid panel ^f			X	X	X	X			

- d Patients who test positive for latent TB at screening, or who have a documented history of a positive TB test but do not have a documented history of at least 4 weeks of appropriate latent TB treatment, may be rescreened (Section 8.4.5). Additionally, patients who do not qualify at screening under exclusion criteria [34, 38, 39, 50] may be rescreened (1 time) as described in Section 5.3.

- k Patients should complete the scales in the following order: 1. GPSS, 2. GPSIS, and 3. SFQ. An e-diary will be used to collect these PROs up to ~~and including~~ Week 12 (V7); thereafter, patients will answer these questions only at scheduled study visits. At Week 12 (V7), patients will complete these scales on site before completion of any other assessments.

- r For the fasting lipid profile patients should not eat or drink anything except water for 12 hours prior to test. (For ETV: [1] If ETV is planned, then fasting lipid profile should be performed, and [2] if ETV is not planned and patient is not fasting, the lipid profile should not be performed.)

Appendix

Page

Appendix 1. Derivation of SF-36v2® Health Survey, Acute Version Scores..... 136

3. Revision History

Statistical Analysis Plan (SAP) Version 1 was approved prior to unblinding. Statistical Analysis Plan Version 2 was approved prior to unblinding, a summary of changes between Version 1 and Version 2 are as follows:

Section	Summary of Changes
4.2 Secondary Objectives 6.4 Multiple Comparisons/Multiplicity 6.10 Efficacy Analyses 6.11 Analysis methodology for primary and major secondary outcomes	Added overall sPGA into major secondary objectives. Added SFQ Item 2 into major secondary objectives. Removed GPSIS Sexual Activity Avoidance Subscale from the major secondary objectives.
4.2 Secondary Objectives Table 6.5	Added change in SF-36 domain score.
6.1 General Considerations	Removed LOCF from analyses on change from baseline. Updated notations of treatment arms in Period 3.
6.1.2 Baseline Definition	Added baseline definition for GPSS, GPSIS, and SFQ, collected by e-diary. Added Multiple as a category for Race.
6.1.3.2 Secondary Analyses Method	Removed LOCF from ANCOVA analyses; removed analyses on effect size for continuous endpoint.
6.3.2 Modified Baseline Observation Carried Forward (mBOCF)	Clarified that the adverse event, mentioned in mBOCF imputation method, will include death.
6.6 Protocol Deviation	Added the category, subcategory, source and programming notes for important protocol deviations.
6.7.1 Demographics and Patient Characteristics	Removed SF-36 Total Score from baseline characteristics.
6.8.1 Previous Therapy	Added Prior Therapy: Genital Psoriasis Entry – Topical Therapy eCRF page into the summary of previous therapy.

Section	Summary of Changes
6.10 Efficacy Analyses	
Updated derivations of GPSS item and total scores at Week 1 (Visit 3), Week 2 (Visit 4), Week 4 (Visit 5), Week 8 (Visit 6), and Week 12 (Visit 7).
 
Updated derivations of GPSS item and total scores at each calendar week in the Blinded Treatment Period.
 
Updated the scoring scheme for GPSIS subscale scores.
 
Updated derivations of GPSIS subscale scores at Week 1 (Visit 3), Week 2 (Visit 4), Week 4 (Visit 5), Week 8 (Visit 6), and Week 12 (Visit 7).
 
Updated derivations of GPSIS subscale scores at each calendar week in the Blinded Treatment Period.
 
Updated derivations of SFQ item scores at Week 1 (Visit 3), Week 2 (Visit 4), Week 4 (Visit 5), Week 8 (Visit 6), and Week 12 (Visit 7).
 
Updated derivations of SFQ item scores at each calendar week in the Blinded Treatment Period.
 
Added exploratory analyses on change from baseline and/or a meaningful improvement from baseline for GPSS, GPSIS, and SFQ at each calendar week in the Blinded Treatment Period.
 
Added exploratory analyses on GPSS Itch score for the change from baseline analyses during the first 14 days, to examine the rapid improvement from baseline in the Blinded Treatment Period.
 
Added exploratory analyses on the association of absence/presence of genital fissure/ulcer/erosion with sPGA of genitalia at Week 12.
 
Added exploratory analyses on the association of absence/presence of genital fissure/erosion/ulcer with measures of quality of life (SF-36 MCS, DLQI, GPSIS Subscales, and SFQ items at Week 12.
 
Added exploratory analyses on the association of absence/presence of perianal/gluteal cleft psoriasis with measures of quality of life (SF-36 MCS, DLQI, GPSIS Subscales, and SFQ items at Week 12.
 
Added exploratory analyses on the association of absence/presence of facial psoriasis with measures of quality of life (SF-36 MCS, DLQI, GPSIS Subscales, and SFQ items at Week 12.

6.15.1 Extent of Exposure	
Added the duration of exposure to ixekizumab treatment for combined treatment period.

Section	Summary of Changes
6.15.2 Adverse Events	Added the overall summary of AEs for combined treatment period.
6.15.3.1 Special Safety Topics including Adverse Events of Special Interest	
Per Ixekizumab Program Safety Analysis Plan Version 7 (IXE PSAP V7):
 
Updated the definition on Elevated hepatic criteria by removing “with all ALP <2× ULN”.
 
Changed category of shift table for ALP from $\geq 1.5 \times \text{ULN}$ to $> 1.5 \times \text{ULN}$ to be consistent with the hepatic elevation tables.
 
Added Medical review to identify allergic reaction/hypersensitivity, opportunistic infection, and IBD.
 
Updated Lilly defined injection site reactions based on MedDRA V19 and removed administration site reactions since the PTs are non-specific.
 
Added new PTs for category Squamous Cell Carcinoma based on MedDRA V19.
 
Updated the Covance reference range to performing lab reference range.
 
Updated Lilly-defined injection site reactions criteria.
 
Added new PTs for category squamous cell carcinoma.
 
Removed analyses for immunoglobulins and segmented neutrophil counts.
 
Changed the baseline definition for neutrophil clinical recovery from Week 0 value to minimum value prior to or at Week 0.
 
Updated the Covance reference range to performing lab reference range.

6.16.2 Immunogenicity Analyses	Updated immunogenicity definitions and terms for clarifications.

4. Study Objectives

4.1. Primary Objective

Primary Objective	Primary Endpoint

 To assess whether 80 mg ixekizumab every 2 weeks (Q2W) is superior to placebo at Week 12 in the treatment of patients with moderate-to-severe genital psoriasis as measured by static Physician’s Global Assessment (sPGA) of Genitalia (0,1) 	
 The proportion of patients achieving sPGA of Genitalia (0,1) at Week 12

4.2. Secondary Objectives

Major Secondary Objectives	Major Secondary Endpoints

 To assess whether 80 mg ixekizumab Q2W is superior to placebo at Week 12 in the treatment of patients with moderate-to-severe genital psoriasis as measured by overall sPGA (0,1) 	
 The proportion of patients achieving overall sPGA (0,1) at Week 12

 To assess whether 80 mg ixekizumab Q2W is superior to placebo at Week 12 in the treatment of patients with moderate-to-severe genital psoriasis as measured by change in itch, utilizing a modified genital psoriasis itch Numeric Rating Scale (NRS) item within the Genital Psoriasis Symptoms Scale (GPSS) 	
 The proportion of patients with at least a 3 point improvement in genital psoriasis itch NRS within the GPSS at Week 12. This will be calculated for patients who had a baseline score of at least 3

 To assess whether 80 mg ixekizumab Q2W is superior to placebo at Week 12 in the treatment of patients with moderate-to-severe genital psoriasis as measured by limitation of frequency of sexual activity due to genital psoriasis, utilizing the SFQ item 2 	
 The proportion of patients whose frequency of sexual activity is never or rarely limited by genital psoriasis, an item score of 0 or 1, at Week 12. This analysis will be done among patients who had a baseline score of at least 2
Other Secondary Objectives	Other Secondary Endpoints

 To assess whether 80 mg ixekizumab Q2W is superior to placebo at Week 12 in the treatment of patients with moderate-to-severe genital psoriasis as measured by impact of genital psoriasis on sexual activity, utilizing the Genital Psoriasis Sexual Impact Scale (GPSIS), Sexual Activity Avoidance Subscale 	
 The proportion of patients whose frequency of avoiding sexual activity is either never or rarely, GPSIS Sexual Activity Avoidance Subscale score of 1 or 2, at Week 12. This will be calculated for patients who had a baseline score of at least 3

 To assess whether 80 mg ixekizumab Q2W is superior to placebo at Week 12 in the treatment of patients with moderate-to-severe genital psoriasis as measured by change in modified Genital Psoriasis Area and Severity Index (mGPASI) 	
 Mean change from baseline in mGPASI at Week 12

Other Secondary Objectives	Other Secondary Endpoints

 • To assess whether 80 mg ixekizumab Q2W is superior to placebo at Week 12 in the treatment of patients with moderate to severe genital psoriasis as measured by the following health outcomes measures: 
 ○ Patient’s Global Assessment of Genital Psoriasis (PatGA-Genital) ○ Dermatology Life Quality Index (DLQI) 
 ▪ Total score ▪ Item 9 ▪ DLQI (0,1) ○ Short form 36 question health survey (SF-36) 
 ▪ physical component summary (PCS) score ▪ mental component summary (MCS) score ▪ 8 domain scores ○ GPSS 
 ▪ Total score ▪ Individual items 	
 ○ The proportion of patients with at least a 2-point improvement from baseline to Week 12 in PatGA-Genital. This analysis will be done among patients who had a baseline score of at least 2. ○ DLQI 
 ▪ Mean change from baseline in DLQI total score at Week 12 ▪ The proportion of patients who with no sexual impairment (i.e. with a DLQI Item 9 score of 0 or 1) at Week 12 ▪ The proportions of patients achieving DLQI (0,1) at Week 12 ○ SF-36 
 ▪ Mean change in SF-36 PCS score and the proportion of patients with at least a 2.5 point improvement at Week 12 ▪ Mean change in SF-36 MCS score and the proportion of patients with at least a 2.5 point improvement at Week 12 ▪ Mean change in SF-36 domain scores at Week 12 ○ Mean change from baseline to Week 12 in 
 ▪ GPSS total score ▪ and individual items

 • Evaluate the incidence of anti-ixekizumab antibodies and its relationship to patient efficacy of ixekizumab at Week 12 	
 • The proportion of patients achieving sPGA of Genitalia (0,1) at Week 12 by treatment emergent anti-drug antibody (TE-ADA) status and by neutralizing anti-drug antibody (NAb) status

 • Time course of response to treatment as measured by sPGA of Genitalia (0,1) 	
 • The proportion of patients who achieve sPGA of Genitalia (0,1) over time through Week 52

 • Time course of response to treatment as measured by mGPASI 	
 • Mean change in mGPASI over time through Week 52

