
 ○ To assess whether 80 mg ixekizumab Q2W is superior to placebo at Week 12 in the treatment of patients with moderate to severe genital psoriasis as measured by the following health outcomes measures: 
 ○ PatGA-Genital ○ DLQI 
 ▪ Total score ▪ Item 9 ▪ DLQI (0,1) ○ SF-36 ○ GPSS 
 ▪ Total score ▪ Individual items ● Evaluate the incidence of anti-ixekizumab antibodies and its relationship to patient efficacy of ixekizumab at Week 12 ● Time course of response to treatment as measured by sPGA of Genitalia (0,1) ● Time course of response to treatment as measured by mGPASI 	
 ○ The proportion of patients with at least a 2-point improvement from baseline to Week 12 in PatGA-Genital ○ DLQI 
 ▪ Mean change from baseline in DLQI total score at Week 12 ▪ Mean change from baseline in DLQI Item 9 score at Week 12 ▪ The proportions of patients achieving DLQI (0,1) ○ Mean change from baseline on the SF-36 PCS and MCS at Week 12 ○ Mean change from baseline to Week 12 in 
 ▪ GPSS total score and ▪ individual items ● The proportion of patients achieving sPGA of Genitalia (0,1) at Week 12 by TE-ADA status and by NAb status ● The proportion of patients who achieve sPGA of Genitalia (0,1) over time through Week 52 ● Mean change in mGPASI over time through Week 52

Exploratory Objectives
 
 ● To assess whether 80 mg ixekizumab Q2W is superior to placebo at Week 12 in the treatment of genital psoriasis patients with baseline BSA $\geq 10\%$ as measured by overall PASI ● To assess whether 80 mg ixekizumab Q2W is superior to placebo at Week 12 in genital psoriasis patients with baseline BSA $\geq 10\%$ as measured by overall PASI 75/90/100 ● To assess whether 80 mg ixekizumab Q2W is superior to placebo at Week 12 in patients with moderate-to-severe genital psoriasis as measured by: 
 ○ sPGA of Genitalia (0) ○ overall sPGA (0) 	
Exploratory Endpoints
 
 ● Mean change from baseline in overall PASI at Week 12 ● The proportion of patients achieving overall PASI 75/90/100 at Week 12 ● The proportion of patients achieving 
 ○ sPGA of Genitalia (0) at Week 12 ○ overall sPGA (0) at Week 12

Objectives	Endpoints

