5.3. Determination of Sample Size

The total sample size for the study will be approximately 146 patients randomized at 1:1 ratio in the Blinded Treatment Period to ixekizumab Q2W and placebo (73 patients per treatment group).

No prior static Physician's Global Assessment (sPGA) of Genitalia (primary outcome measure) data was available at the time of planning this study to guide sample size and power calculations because no biologic drug has been evaluated in a well-controlled clinical trial to date in patients with genital psoriasis. Therefore, based on the relevance and impact of sexual impairment in genital psoriasis, data from the assessment of the Dermatology Life Quality Index (DLQI) Item 9 (How much has your skin caused any sexual difficulties?) outcomes in the ixekizumab Phase 2 and Phase 3 studies were used to calculate the sample size. Sample size was calculated assuming sexual impairment rates of 2% and 20% in the ixekizumab Q2W and placebo treatment groups, respectively. With these assumed rates, a sample size of 146 (73 per treatment group) is likely to achieve 94% power, based on a 2-sided Fisher's exact test at 0.05 level of significance.

6. A Priori Statistical Methods

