PatGA-Genital	The Patient’s Global Assessment of Genital Psoriasis (PatGA-Genital) is a patient-administered, single-item scale on which patients are asked to rank the severity	PatGA-Genital score	The PatGA-Genital NRS score as reported by the patient. The score ranges from 0 to 5.	Missing if the PatGA-Genital score is missing

Measure	Description	Variable	Derivation	Imputation Approach if Components are Missing
	of their genital psoriasis “today” by circling a number on a 0 to 5 NRS, as follows: from 0 (clear), no genital psoriasis; to 5 (severe).	2 point improvement in PatGA-Genital score	First calculate $\text{Change from baseline} = \text{Observed PatGA Genital score} - \text{Baseline PatGA Genital score}$ If change from baseline is less than or equal to -2, then the patient has experienced a 2-point improvement. If change from baseline is greater than -2, then the patient has not experienced a 2-point improvement.	Missing if the observed or baseline PatGA Genital score is missing
DLQI	The DLQI is a simple, patient-administered, 10 question, validated, quality-of-life questionnaire that covers 6 domains: 
 1. Symptoms and feelings 2. Daily activities 3. Leisure 4. Work and school 5. Personal relationships 6. Treatment Response categories include 0 = not at all 1 = a little 2 = a lot and 3 = very much “not relevant” responses scored as “0”.	DLQI total score	A DLQI total score is calculated by summing all 10 question responses, and has a range of 0 to 30 (less to more impairment). (Finlay and Khan 1994; Basra et al. 2008).	If two or more questions are missing, the total score is missing.
		Change from baseline in DLQI total score	$\text{Change from baseline} = \text{Observed DLQI Total score} - \text{Baseline DLQI Total score}$ A negative change indicates improvement and a positive change indicates deterioration of the condition.	Missing if the observed or baseline DLQI Total score is missing
	DLQI Item 9 asks the following: How much has your skin caused any sexual difficulties?	DLQI Item 9 score	DLQI item 9 score as reported by the patient.	Missing if the DLQI item 9 score is missing

Measure	Description	Variable	Derivation	Imputation Approach if Components are Missing
		No Sexual Impairment	A DLQI Item 9 score of 0 or 1	Missing if the DLQI item 9 score is missing

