PatGA-Genital	Proportion of patients with at least a 2-point improvement in PatGA-Genital	ITT Population: Patients with a baseline score of at least 2	Week 12 and other post-baseline visits	Logistic regression analysis using NRI	Other secondary	Primary
			Week 12 and other post-baseline visits	Fisher's exact test using NRI		Secondary

Measure	Variable	Population (Section 6.1.1)	Time Point	Analysis and Imputation Method (Sections 6.1.3 and 6.3)	Objective/ Endpoint Type	Analysis Type
DLQI	Change from baseline in DLQI total score	ITT Population	Week 12 and other post-baseline visits	MMRM	Other secondary	Primary
			Week 12 and other post-baseline visits	ANCOVA using mBOCF		Secondary
	Proportion of patients with no sexual impairment	ITT Population	Week 12 and other post-baseline visits	Logistic regression analysis using NRI	Other secondary	Primary
			Week 12 and other post-baseline visits	Fisher’s exact test using NRI		Secondary
	Proportion of patients with DLQI(0,1)	ITT Population	Week 12 and other post-baseline visits	Logistic regression analysis using NRI	Other secondary	Primary
			Week 12 and other post-baseline visits	Fisher’s exact test using NRI		Secondary
SF-36	Change from baseline in SF-36 PCS score	ITT Population	Week 12 and other post-baseline visits	ANCOVA using mBOCF	Other secondary	Secondary

Measure	Variable	Population (Section 6.1.1)	Time Point	Analysis and Imputation Method (Sections 6.1.3 and 6.3)	Objective/Endpoint Type	Analysis Type
	Proportion of patients with at least a 2.5 point improvement in SF-36 PCS	ITT Population	Week 12 and other post-baseline visits	Logistic regression analysis using NRI	Other secondary	Primary
			Week 12 and other post-baseline visits	Fisher’s exact test using NRI		Secondary
	Change from baseline in SF-36 MCS score	ITT Population	Week 12 and other post-baseline visits	ANCOVA using mBOCF	Other secondary	Secondary
	Proportion of patients with at least a 2.5 point improvement in SF-36 MCS	ITT Population	Week 12 and other post-baseline visits	Logistic regression analysis using NRI	Other secondary	Primary
			Week 12 and other post-baseline visits	Fisher’s exact test using NRI		Secondary
	Proportion of patients with at least a 5 point improvement in SF-36 individual domain scores	ITT Population	Week 12 and other post-baseline visits	Logistic regression analysis using NRI	Other secondary	Primary
			Week 12 and other post-baseline visits	Fisher’s exact test using NRI		Secondary

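### The SAP omits the protocol's mean change in DLQI Item 9 and substitutes a 0-or-1 proportion whose label, 'no sexual impairment', contradicts its own scale

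*SAP*

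**What the plan says.** - Protocol Table RHBQ.3.1 (Section 3), other secondary endpoints: "Mean change from baseline in DLQI Item 9 score at Week 12".
- SAP Section 4.2 keeps the Item 9 objective but gives as its endpoint: "The proportion of patients who with no sexual impairment (i.e. with a DLQI Item 9 score of 0 or 1) at Week 12".
- SAP Table RHBQ.6.4 lists the DLQI response categories as "0 = not at all 1 = a little 2 = a lot and 3 = very much" and derives the variable named No Sexual Impairment as "A DLQI Item 9 score of 0 or 1". It derives change from baseline for the DLQI total and domain scores. Item 9 appears only as the reported score and this dichotomy.
- SAP Table RHBQ.6.5 has a row "Proportion of patients with no sexual impairment", run on the whole ITT population by logistic regression with NRI and then by Fisher's exact test. The only DLQI change row is for the total score.
- The sample-size text (Protocol 9.1, SAP 5.3) also draws on Item 9: "Sample size was calculated assuming sexual impairment rates of 2% and 20% in the ixekizumab Q2W and placebo treatment groups, respectively". On those rates, "a sample size of 146 (73 per treatment group) is likely to achieve 94% power". It does not say which Item 9 scores count as impairment.

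**The concern.** There are two separate problems. First, protocol and SAP name different endpoints for one objective, and the SAP plans nothing that would yield the protocol's version. The SAP was not working from an outdated protocol: its Section 6.8.2 cites amendment (b), whose current Table RHBQ.3.1 still specifies mean change.

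Second, the name given to the substitute does not match what it counts. A reader of the study report would take a percentage with no sexual impairment to mean patients without sexual difficulty. It would include patients who said their skin caused a little. Item 9 bears directly on the trial's subject, and the sponsor chose it as the basis for the sample size, so this percentage is likely to be read and repeated.

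**Working it through.** **1. The plan's own Item 9 figure.** Inputs from SAP 5.3: 73 per arm, impairment 2% v 20%, two-sided Fisher's exact test at 0.05. Exact power is the sum over all pairs (i, j) of Bin(i; 73, 0.02) × Bin(j; 73, 0.20), counting pairs with Fisher p ≤ 0.05. The result is 94.7%; a normal approximation gives 94.3%. The stated 94% reproduces. This shows that a binary Item 9 outcome has precedent in the plan. It does not settle the cut-point.

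**2. Is change in Item 9 planned anywhere in the SAP?**

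| Place | Item 9 content |
|---|---|
| SAP 4.2 | proportion scoring 0 or 1 |
| SAP 6.7.1 | baseline Item 9 score, descriptive |
| Table RHBQ.6.4 | reported score; 0-or-1 dichotomy; no change variable |
| Table RHBQ.6.5 | proportion only; change row is DLQI total |

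SAP 6.1.3.1 applies MMRM to all continuous outcomes, but with no change variable derived and no row listed, nothing directs it to Item 9. The personal-relationships domain change adds Items 8 and 9 together and is not a substitute.

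**3. Does the proportion carry the same information?** With four levels there are 4 × 4 = 16 baseline-to-Week-12 pairs. Six are improvements: 1→0, 2→0, 2→1, 3→0, 3→1 and 3→2. Eight pairs end at 0 or 1 and count as success:
- five are improvements (all of the above except 3→2, which counts as failure);
- two are no change (0→0, 1→1);
- one is a worsening (0→1).

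The two endpoints answer different questions: status at Week 12 against change since baseline.

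**4. Size of the labelling error.** Let p0 and p1 be an arm's Week 12 proportions scoring 0 and 1. The reported figure is p0 + p1; the proportion with no difficulty is p0; the excess is p1. One patient is worth 1/73 = 1.4 points. Suppose, as an assumption, that the sample-size text uses the SAP's cut, so that impairment means 2 or 3. The reported figures would then be 100 − 2 = 98% and 100 − 20 = 80%, a difference of 18 points. The excess p1 could lie anywhere from 0 to 98 points and from 0 to 80 points respectively, so the documents give no useful bound. The distortion of the between-arm difference is p1(ixekizumab) − p1(placebo), whose sign is also unknown.

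**5. Can the protocol endpoint be produced?** The Schedule of Activities collects DLQI at Weeks 0, 2, 4, 8 and 12. That supplies a baseline and four post-baseline visits for the SAP's standard MMRM.

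**The case against.** The best defence is that a responder form suits a four-level ordinal item, that the 0-or-1 definition is printed beside the label, and that baseline Item 9 is tabulated by arm. The endpoint is other-secondary and outside the testing sequence in SAP 6.4. Sexual impact is also tested through SFQ Item 2, a major secondary endpoint, and through GPSIS avoidance. All of this is true and limits the consequence. It supports keeping the proportion as an extra analysis. It does not produce the protocol's endpoint or make a score of 1 mean none.

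A reader might infer three stronger points that the documents do not support.

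- **That the absence of a baseline filter is an error that dilutes the effect.** SFQ Item 2 is filtered ("This analysis will be done among patients who had a baseline score of at least 2"), as are itch, GPSIS and PatGA-Genital. But DLQI (0,1) and the SF-36 responder endpoints in Table RHBQ.6.5 are not, so there is no uniform rule to breach. A patient at 0 both at baseline and at Week 12 is correctly counted as without difficulty at Week 12. Mean change in all patients is diluted too, since those starting at 0 cannot improve. The size cannot be computed because the baseline Item 9 distribution is not given. As an illustration, assume patients starting at 0 or 1 stay there in both arms and a fraction f start at 2 or 3. If 2% and 20% are all-patient rates, the difference among those starting at 2 or 3 is 18/f: 22.5 points at f = 0.8 and 45 at f = 0.4, with power 94.9% and 97.8% against 94.7% unrestricted. If they are rates among those starting at 2 or 3, the all-patient difference is 18 × f: 14.4 and 7.2 points, with power 86% and 38% whether restricted or not. At f = 0.3 the gap on this second reading widens, to 20% unrestricted against 33% restricted. The filter is a choice of estimand.
- **That the change went unlogged.** The SAP revision history covers only Version 1 to Version 2. If Version 1 already held the proportion, no entry was due. Protocol 9.2 asks for an amendment only when a principal feature changes; other changes to analysis methods are to be justified in the study report.
- **That scoring 'not relevant' as 0 is a fault of this endpoint.** It is the protocol's own DLQI scoring (Section 8.1.2.2.5) and would affect mean change equally.

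**Conclusion.** The point holds in two parts, both wrong as written. The protocol's Item 9 endpoint has no planned analysis in the SAP, and the substitute's label contradicts the SAP's response scale. Both follow from the text and need no assumption. The excess in each arm's reported percentage equals the share scoring exactly 1 at Week 12, at 1.4 points per patient with 73 per arm; the documents do not allow an estimate beyond that.

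The impact is limited to this endpoint's fidelity and interpretation. The randomised comparison of the 0-or-1 proportion is unbiased, and neither the primary conclusion nor the multiplicity-controlled sequence is touched.

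**What to change.** 1. Add mean change from baseline in DLQI Item 9 to SAP 4.2, to Table RHBQ.6.4 (observed minus baseline, missing if either is missing) and to Table RHBQ.6.5. Analyse it by the standard MMRM at Weeks 2, 4, 8 and 12, with ANCOVA using mBOCF as the secondary method, as is already done for the DLQI total.
2. Keep the 0-or-1 proportion as supportive, renamed 'no or little sexual difficulty'. Alternatively, define 'no sexual impairment' as a score of 0.
3. Optionally, add a supportive version of the proportion in patients with baseline Item 9 of at least 2, matching SFQ Item 2. This is not a correction, and it has a smaller denominator.

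The cost is one added analysis and one relabelled row, with no new data collection. Make the change before the Week 12 database lock and sponsor unblinding described in SAP 6.18.
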